a The last day of dosing will be at Week 36 visit; subject should consume their last dose of study drug on site, after pre-dose assessments have been completed. The Week 36 visit will also be the ET visit. During the study visit, assessments should be collected from any subject who discontinues study drug or study prematurely. Early termination visits will have the same procedures as the Week 36 visit, except that study drug will not be administered and trough PK will not be collected.

b The first day study drug is taken is considered Baseline (Day 1). Day 1 assessments should be performed prior to study drug administration. If a subject requires a transfusion on this day, the transfusion may occur only after all study assessments are completed.

c Qualified site personnel will contact the subject by telephone at Week 2 to capture potential TEAEs and concomitant medications. Subjects will also be reminded of compliance with drug and the next visit schedule. If any AEs of significant clinical concern are identified during the telephonic visit, the subject will be requested to come into the site to be assessed.

d Pharmacogenomic evaluation is optional and may be performed at screening if subject provides informed consent.

e Disease history should contain a confirmed diagnosis of  $\beta$ -thalassemia or hemoglobin E/ $\beta$ -thalassemia. Concomitant alpha gene deletion, duplication, or triplication is allowed.

f After obtaining signed informed consent, the subject's transfusion history for the 12 weeks prior to Baseline (Day 1) visit date should be recorded. In order to be eligible for the study, the dates of transfusion events and the number of pRBC units per event within the 12 weeks prior to the Baseline (Day 1) visit must be available. If available, the following data should also be collected for each transfusion event: volume and hematocrit of each pRBC unit, pre-transfusion Hb, and pre-transfusion weight.

g Vital signs include heart rate, respiratory rate, blood pressure, and body temperature. At Day 1 and Week 3, vital signs will be taken pre-dose and 2 hours ( $\pm$  20 minutes) post-dose, during the PK assessments. At all other timepoints, vital signs can be taken irrespective of taking study drug. Vital signs should be consistently measured in either the sitting or semi-supine position.

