## **8.5. Guidelines for Study Drug Dose Withholding or Discontinuation**

### **8.5.1. Safety Criteria for Study Dose Interruption or Discontinuation**

In consultation with the medical monitor, the investigator may decide to withhold the study drug or withdraw the subject in cases where tolerability or safety concerns emerge. Table 4 provides recommended guidelines for these decisions.

If a study drug dosing is withheld due to an AE (Section 12), subjects who continue on the study will have all assessments (except study drug administration) performed as per protocol.

If study drug dosing is discontinued for any reason, the specific circumstances surrounding the discontinuation must be recorded in the subject's eCRF. Any subject who discontinues study drug dosing must also be withdrawn from the study; however, all appropriate safety assessments and follow-up should be completed prior to withdrawal (Section 8.4).

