### 9.7.2. Prohibited Concomitant Medications/Therapies

The investigator, in consultation with the medical monitor, will determine if any of the following concomitant medications/therapies are necessary for the well-being of the subject. The subject will be withdrawn from the study if the following are determined to be necessary:

- PDE5 inhibitors; any drugs or substances, including grapefruit juice or herbal supplements with CYP altering properties, that are known to strongly or moderately inhibit or induce CYP/CYP3A enzymes; and any drugs or substances that are substrates or significant inhibitors of P-gp or BCRP. Sensitive substrates of CYP3A4/5 are also prohibited. If there is any question as to whether a substance is permitted, please review the product labeling (if applicable), and consult the medical monitor and/or sponsor.

- Concomitant use of erythropoietin.
- Any concomitant use of sotatercept or luspatercept (Reblozyl®), or previous use within 6 months prior to randomization (Day 1).
- Any other investigational drug or device.

Because IMR-687 is a CYP3A4 substrate as well as a possible CYP3A4 inducer, caution should be employed in the co-administration of IMR-687 with other medications that are known CYP3A4 substrates. This potentially helps manage the competition for in vivo CYP3A4-mediated clearance, which could result in a DDI. This approach includes applying caution with dosing other oral medications to minimize the chance of a drug interaction at the site of absorption (e.g., the GI tract). Additional information on potential drug interactions and how to proceed can be found in Section [5.2.3](#).

Medications prohibited prior to study entry are described in the exclusion criteria in Section [8.2](#).

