6.1 Changes from Protocol

In this SAP three analysis sets were added - the Intent-to-Treat (ITT) Analysis Set, which is defined in Section 11.2, the Modified Intent-to-Treat (mITT) Analysis Set, which is defined in Section 11.3, and the PK Evaluable Set, which is defined in Section 11.6. The ITT and mITT Analysis Sets were added to summarize the efficacy analysis. The ITT Analysis set will allow for an assessment of all randomized subjects. The mITT Analysis set allows for an assessment of all randomized subjects who received at least one dose of study drug, regardless of their compliance with or any deviations from the protocol. The Per Protocol (PP) Analysis Set definition in Section 11.4 has been clarified to include subjects with any post-baseline assessment and who did not discontinue prior to week 12 for reasons other than AEs.

The definition of the Safety Analysis Set was clarified to remove the requirement for the subject to give informed consent. This does not change the definition in practice as all subjects in the Safety Analysis Set are required to receive at least one dose of study drug which would only happen after the subject gave informed consent.

The definition of the PK analysis set was modified. As per protocol, the PK Analysis Set was defined as a subset of the Safety Analysis Set that included all subjects who were enrolled in the study, received at least 1 dose of IMR-687, and had sufficient IMR-687 concentration data to be used in the PK analyses. This has been further delineated with the addition of a PK Evaluable Set and for each of these PK population subsets, the definitions were updated as follows:

- The PK Analysis Set, will be defined as a subset of the Safety Analysis Set that includes all subjects who are enrolled in the study, have received at least 1 dose of IMR-687, and have any measurable post-dose IMR-687 concentration-time data. This set will be used to generate the corresponding PK concentration summaries and plots.
- The PK Evaluable Set will be defined as all subjects in the Safety Analysis Set who are randomized, have received at least 1 dose of IMR-687, and have at least 4 consecutive non-zero post-dose IMR-687 concentration-time data points. The PK Evaluable Set will be used to generate the corresponding PK parameter assessments.

An interim analysis was added (IA 0.5) for the NTDT population to be performed when approximately 15 NTDT subjects have completed 12 weeks of treatment.

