Week 12 (Day 84 ± 7)	54 to 106
Week 18 (Day 126 ± 7)	107 to 148
Week 24 (Day 168 ± 7)	149 to 211
Week 36 (Day 252 ± 7)	≥212
QoL	
Scheduled Study Visit (Protocol Scheduled Day)	Analysis Visit Window (Study Day)
Baseline	≤ 1
Week 12 (Day 84 ± 5)	2 to 127
Week 24 (Day 168 ± 7)	128 to 211
Week 36 (Day 252 ± 7)	≥212

Table 2: Visit Windows for Efficacy and Safety Analyses – NTDT Population

Safety Analyses – Vital Signs, Weight, 12-Lead ECG, Hematology (Except Specialty Hematology) and Chemistry	
Scheduled Study Visit (Protocol Scheduled Day)	Analysis Visit Window (Study Day)
Baseline	≤ 1
Week 1 (Day 7 ± 2)	2 to 18
Week 4 (Day 28 ± 5)	19 to 43
Week 8 (Day 56 ± 7)	44 to 71
Week 12 (Day 84 ± 7)	72 to 99
Week 16 (Day 112 ± 7)	100 to 127
Week 20 (Day 140 ± 7)	128 to 155
Week 24 (Day 168 ± 7)	156 to 183
Week 28 (Day 196 ± 7)	184 to 211
Week 32 (Day 224 ± 7)	212 to 239
Week 36 (Day 252 ± 7)	240 to 267
Week 40 (Day 280 ± 7)	≥ 268
Safety Analyses – Urinalysis	
Scheduled Study Visit (Protocol Scheduled Day)	Analysis Visit Window (Study Day)
Baseline	≤ 1
Week 4 (Day 28 ± 5)	2 to 57
Week 12 (Day 84 ± 7)	58 to 127
Week 24 (Day 168 ± 7)	128 to 211
Week 36 (Day 252 ± 7)	≥212
Safety Analyses – Coagulation	
Scheduled Study Visit (Protocol Scheduled Day)	Analysis Visit Window (Study Day)
Baseline	≤ 1
Week 12 (Day 84 ± 7)	2 to 127
Week 24 (Day 168 ± 7)	128 to 211
Week 36 (Day 252 ± 7)	≥212
Efficacy Analyses – Specialty Hematology	
Scheduled Study Visit (Protocol Scheduled Day)	Analysis Visit Window (Study Day)
Baseline	≤ 1
Week 4 (Day 28 ± 5)	2 to 57

Week 12 (Day 84 ± 7)	58 to 127
Week 24 (Day 168 ± 7)	128 to 211
Week 36 (Day 252 ± 7)	≥212
Efficacy Analyses- PD Biomarkers	
Scheduled Study Visit (Protocol Scheduled Day)	Analysis Visit Window (Study Day)
Baseline	≤ 1
Week 4 (Day 28 ± 5)	2 to 57
Week 12 (Day 84 ± 7)	58 to 127
Week 24 (Day 168 ± 7)	128 to 211
Week 36 (Day 252 ± 7)	≥212
QoL	
Scheduled Study Visit (Protocol Scheduled Day)	Analysis Visit Window (Study Day)
Baseline	≤ 1
Week 12 (Day 84 ± 5)	2 to 127
Week 24 (Day 168 ± 7)	128 to 211
Week 36 (Day 252 ± 7)	≥212

Windowing will be applied prior to any missing data calculations. The last non-missing measurement taken prior to the date of first dose (including unscheduled assessments) will be labeled as “Baseline”. Screening visits that occurred before the Baseline visit will not be assigned an analysis visit. The early discontinuation visit will be eligible for allocation to an analysis visit.

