13.6.3 Imputation Methods for Endpoints

Unless otherwise specified, no imputation of data relating to the primary endpoint of safety and tolerability, or for secondary or exploratory efficacy endpoints, will be performed.

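### Stopping study drug means leaving the study, so stoppers have truncated or empty Week 12-24 and Week 24-36 windows, and the SAP has no rule for an incomplete transfusion window

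*Protocol*

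**What the plan says.** Protocol 8.5.1 ties the two events together: "Any subject who discontinues study drug dosing must also be withdrawn from the study". Before the subject leaves, "all appropriate safety assessments and follow-up should be completed prior to withdrawal"; efficacy follow-up is not named. A temporary hold is treated differently: "subjects who continue on the study will have all assessments (except study drug administration) performed as per protocol". Study withdrawal is also prescribed in Table 4 (recurrence after the original dose is resumed, or as an option when a longer hold is needed), in 9.7.2 ("The subject will be withdrawn from the study if the following are determined to be necessary") and in 10.4 (after unblinding).

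Some data are still collected. Table 2, footnote a, says: "Early termination visits will have the same procedures as the Week 36 visit, except that study drug will not be administered". The Week 36 procedures include transfusion burden, hematology, specialty hematology, PD markers and QoL. The follow-up visit schedules transfusion burden and hematology. SAP 10.1.10 adds: "The early discontinuation visit will be eligible for allocation to an analysis visit".

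SAP 6.1 introduces the ITT set with this purpose: "The ITT Analysis set will allow for an assessment of all randomized subjects". SAP 11.4 and 13.6.4 make per protocol (PP) the primary efficacy set and ITT a sensitivity analysis. SAP 13.6.3 sets a default, open to exceptions stated elsewhere in the SAP: "no imputation of data relating to the primary endpoint of safety and tolerability, or for secondary or exploratory efficacy endpoints, will be performed". SAP 13.0 bases percentages on the number in the analysis set unless otherwise specified. SAP 13.6.4.1 defines transfusion burden as the sum of units in the 12- or 24-week period.

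**The concern.** The main transfusion and hemoglobin responder endpoints are defined over Weeks 12-24 and 24-36. A subject who stops drug early is out of the study for part or all of those windows. An ITT analysis is useful as a check on a per protocol result only if outcomes are known for people who stopped. Here the outcomes that would separate the two analyses are largely not collected.

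Stopping may also differ by arm. Protocol 4.2.3.1 reports nausea in 35% of IMR-687 subjects v 0% on placebo when fasted, and dose-limiting emesis at 6 mg/kg. Food reduced these events, so the size of any imbalance in this trial is unknown.

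The problem is not confined to ITT. The PP data-sufficiency rule in SAP 11.4 removes subjects who leave before Week 12 only if the reason was not an AE. An early AE stopper with any post-baseline assessment can therefore stay in the primary efficacy set with an empty window and no defined responder status.

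**Working it through.** **1. What is observed after a stop.** Protocol synopsis: the follow-up assessment is 4 weeks after the last dose. If that visit takes place, data end about 4 weeks after stopping.

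- Week 12-24 window empty if stopping + 4 is at or before 12, that is, stopping by about Week 8.
- Week 24-36 window empty if stopping + 4 is at or before 24, that is, stopping by about Week 20.
- Later stops leave a truncated window.

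**2. The plan's own figure.** SAP 8.1.1 gives about 79% power for 10% v 50% with 20 placebo and 30 active subjects, two-sided 0.05. With a pooled null variance and continuity correction:

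- Pooled rate = (20 × 0.10 + 30 × 0.50)/50 = 0.34.
- Null SE = √(0.34 × 0.66 × (1/20 + 1/30)) = 0.1367.
- Correction = 0.5 × (1/20 + 1/30) = 0.0417.
- Alternative SE = √(0.09/20 + 0.25/30) = 0.1133.
- z = (0.40 − 0.0417 − 1.96 × 0.1367)/0.1133 = 0.797, so power = 78.7%.

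The same formula gives 66.6% for NTDT (stated 67%, 15 v 30). Both reproduce, and neither allows for loss. As an illustration, Protocol 8.6 lets up to 10 of about 60 subjects per population be replaced. A 16.7% loss (10/60), equal in both arms and not made up by replacement, cuts complete-case power to 67.5% (TDT) and 53.9% (NTDT).

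**3. TDT stoppers with units summed as observed.** Let b be the units in the 12 weeks before baseline, the transfusion rate be unchanged, and data end at Week w. Units counted in Weeks 12-24 = b × (w − 12)/12.

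| b | w | Units counted | Reduction | Criteria met, with at least 2 units |
|---|---|---|---|---|
| 4 | 18 | 2.0 | 2.0 (50%) | 20%, 33%, 50% |
| 6 | 20 | 4.0 | 2.0 (33.3%) | 20%, 33% |
| 8 | 21 | 6.0 | 2.0 (25%) | 20% |
| 10 | 21 | 7.5 | 2.5 (25%) | 20% |

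Each is a response created only by missing weeks. Eligible TDT subjects have more than 3 and up to 10 units, so this covers the trial's range. A constant rate is a simplification, since units are given in whole bags.

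**4. Stoppers dropped.** Assumptions, none from the documents: no drug effect, true response 30% in both arms, 20% of active and 5% of placebo subjects stop, and every stopper is a non-responder. Arm sizes are those of SAP 8.1.1.

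- Active: 0.30/0.80 = 37.5%, on 30 × 0.80 = 24 subjects.
- Placebo: 0.30/0.95 = 31.6%, on 20 × 0.95 = 19 subjects.
- Spurious difference: 5.9 points.
- CMH size by full enumeration, two-sided 0.05: 4.5% at 30 v 20 with no loss, and 6.5% at 24 v 19.
- With 25% v 10% stopping: 0.30/0.75 − 0.30/0.90 = 40.0% − 33.3% = 6.7 points.

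**5. Stoppers kept in the denominator as non-responders.** In the scenario of step 4 the rates are 30% v 30% and the size is 4.5%. This is one reading of the denominator rule in SAP 13.0.

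Steps 3 to 5 apply three different treatments to the same kind of subject. For the fixed transfusion windows the SAP does not say which one applies.

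**The case against.** The strongest reply is that the plan is fuller than 8.5.1 alone suggests, and much of that stands.

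- A reader might infer that no efficacy data exist after stopping. The documents do not support this. The early termination and follow-up visits collect transfusion and hematology data, the early visit can be mapped to an analysis visit, and Protocol 8.4 asks for follow-up medical records if a final visit is not feasible.
- A reader might infer that nothing is imputed. SAP 13.6.4.2 and 13.6.6.2 give rules for the NTDT endpoints: transfusion and partly missing values for Hb and HbF in the first, and Hb in the second. SAP 13.6.4.1 uses the last 12 weeks on drug for chelation dose and ferritin in early stoppers. None of these rules settles a TDT subject's truncated or empty transfusion window, or an NTDT subject with no Hb in the window.
- A reader might infer that every efficacy endpoint is affected. Rolling-window responders, cumulative transfusion events, transfusion independence and time to first Hb increase all use data from before the stop and are less affected.
- A reader might take 37.5% v 31.6% as the ITT result. It holds only if stoppers are dropped. Under the analysis-set denominator the bias disappears in that scenario.

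It is also fair to say that safety is the primary objective, the sample size is not driven by efficacy, and ITT is a sensitivity analysis. Whether to follow people after they stop is partly a design choice. That limits the importance of the point. It does not supply the missing outcomes or the missing rule.

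**Conclusion.** The concern holds in a limited form. For the fixed-window Week 12-24 and 24-36 endpoints, mandatory study withdrawal leaves stoppers with truncated or empty windows, and the ITT analysis cannot give the assessment of all randomized subjects that SAP 6.1 describes. For TDT the direction of error depends on an unstated choice: summing observed units can create responders, dropping stoppers can favour the arm with more stopping, and counting them as non-responders removes the bias in the scenario examined.

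The sizes are illustrations. The false response at 6 units with data ending at Week 20 assumes a constant rate and summation as observed. The 5.9-point gap and the rise in size from 4.5% to 6.5% rest on assumed stopping rates, an assumed 30% response, and stoppers all being non-responders. The documents give no expected stopping rate. This is a worthwhile, low-cost improvement to secondary efficacy analyses and does not affect the primary safety objective.

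**What to change.** **Protocol.** In 8.5.1, state that stopping study drug is not withdrawal from the study. Unless consent is withdrawn, keep collecting transfusion dates and units through Week 36 (from records or by telephone) and, for NTDT, Hb and HbF at the remaining scheduled visits. Align the withdrawal wording in Table 4, 9.7.2 and 10.4 for data collection only, so that the protocol does not contradict itself. Nothing about when drug is held or stopped changes.

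**SAP.** In 11.2, state that ITT uses all collected data regardless of stopping. In 13.6.4.1, state that a subject whose transfusion window is incomplete is not counted as a responder on the basis of unobserved weeks, and apply the same rule to the rolling windows. This rule is still needed after the protocol change, because some subjects will withdraw consent.

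**Cost.** A short amendment and a few extra data contacts for those who stop. Procedures for assessing subjects off drug already exist for temporary holds. The ITT estimate will include off-drug time and may be slightly smaller.

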**Table 4: Safety Guidelines for Study Dose Reduction, Interruption, or Discontinuation**

Dose Reduction	
Event	Recommended Action
A Grade 2 or higher TEAE that, in the opinion of the investigator, is both study drug related and that makes continued dosing at the current dose level inadvisable due to safety concern or lack of tolerability.	
Study drug may be reduced by one tablet for up to 14 continuous days.
 
If, in the opinion of the investigator, a longer dose reduction is clinically needed, the medical monitor should be contacted.
 
If, in the opinion of the investigator, the severity of the Grade <math>\geq 2</math> TEAE has reduced to Grade <math>\leq 1</math>, the subject may resume study drug at the original dose. If the TEAE recurs after re-introduction of the original dose, the subject should be withdrawn from the study.

Dose Interruption (Hold)	
Event	Recommended Action
A Grade 3 or higher TEAE that, in the opinion of the investigator, is both study drug related and that makes continued dosing at the current dose level inadvisable due to safety concern or lack of tolerability.	
Study drug should be held for up to 7 continuous days until reduction in severity of the TEAE to Grade <math>\leq 2</math>, then resumed at the original dose.
 
If, in the opinion of the investigator, dosing should be resumed at a lower dose, the medical monitor should be contacted.
 
If, in the opinion of the investigator, a longer dose hold is clinically needed, the medical monitor should be contacted or the subject should be withdrawn from the study.

Positive test results for COVID-19 and/or similar illness (asymptomatic and symptomatic).	Study drug should be held until 7 days after subject tests negative. Please consult with the medical monitor if there are any questions.

COVID-19 = coronavirus disease 2019; TEAE = treatment-emergent adverse event.

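### Protocol Table 4 sets a looser default for return to full dose after a hold for a related Grade 3 or higher event than after a reduction for a related Grade 2 or higher event

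*Protocol*

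**What the plan says.** Protocol Section 8.5.1 places the decision with the investigator and medical monitor ("In consultation with the medical monitor, the investigator may decide to withhold the study drug or withdraw the subject") and makes the table advisory: "Table 4 provides recommended guidelines for these decisions".

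The dose reduction row of Table 4 is triggered by "A Grade 2 or higher TEAE that, in the opinion of the investigator, is both study drug related" and makes the current dose inadvisable. Its action is optional: "Study drug may be reduced by one tablet for up to 14 continuous days". Return to full dose depends on severity having fallen to Grade ≤1, and the row then reads: "the subject may resume study drug at the original dose. If the TEAE recurs after re-introduction of the original dose, the subject should be withdrawn".

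The dose interruption row has the same two conditions but starts at Grade 3. Its action is "Study drug should be held for up to 7 continuous days until reduction in severity of the TEAE to Grade" 2 or lower, followed by the original dose. The same cell adds: "If, in the opinion of the investigator, dosing should be resumed at a lower dose, the medical monitor should be contacted". If a longer hold is needed, the choice is to contact the medical monitor or withdraw the subject. The row does not mention recurrence after restart.

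**The concern.** A return-to-dose rule would normally be at least as demanding after a worse event. Here a subject held for a related Grade 3 or 4 event goes back by default to both tablets while the event may still be Grade 2. Section 12.1.2.2.1 of the protocol defines Grade 2 as moderate and limiting instrumental daily activities. Grade 2 is also the severity at which the reduction row opens. A subject whose related event never passed Grade 2, and who was reduced for it, must reach Grade 1 before full dose may resume.

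What is at stake is the safety of individual subjects and like handling of like events across about 50 sites. The estimation of the primary safety endpoint is not affected.

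**Working it through.** The core of the point is a comparison of text, so the two rows are set side by side.

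| | Dose reduction row | Dose interruption row |
|---|---|---|
| Trigger (related, dosing inadvisable) | Grade ≥2 | Grade ≥3 |
| Action | may drop one tablet, up to 14 days | should hold, up to 7 days |
| Dosing when recovery is judged | one tablet daily | none |
| Full dose resumes at | Grade ≤1 | Grade ≤2 |
| Recurrence at full dose | withdraw | not stated |

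The first action is ordered correctly: a hold that should happen is stricter than a reduction that may happen. The ordering fails only at the return to full dose and in the recurrence line. Grading off drug does not explain the looser threshold, because an event still at Grade 2 without drug gives no assurance about full dose. Protocol Sections 8.4, 8.5.1 and 8.7 and the SAP contain nothing that changes the Grade ≤2 threshold.

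**Dose at restart** (tablet strengths and 60 kg gate from Protocol Section 9.2; 45 kg minimum weight from exclusion criterion 4). The highest mg/kg values are:
- Higher dose, 45 kg: 2 × 150 / 45 = 6.67 mg/kg on two tablets; 150 / 45 = 3.33 on one.
- Higher dose, 60 kg: 2 × 200 / 60 = 6.67 mg/kg; 200 / 60 = 3.33 on one.
- Lower dose, 60 kg: 2 × 150 / 60 = 5.00 mg/kg; 150 / 60 = 2.50 on one.

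**Exposure cost of a one-tablet restart.** Planned tablets: 36 weeks × 7 days × 2 = 504. One tablet fewer per day for the existing 14-day cap: 14 tablets, and 14 / 504 = 2.8%. The 7-day hold already in the plan also costs 7 × 2 = 14 tablets, and the change does not lengthen it.

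**Why a bare Grade ≤1 rule would not work.** NTDT subjects enter with Hb ≤10.0 g/dL (Protocol Section 8.1, criterion 10). SAP Appendix 4 grades Hb below 10.0 down to 8.0 g/dL as Grade 2 anemia and below 8.0 as Grade 3. An NTDT subject below 10.0 g/dL at entry therefore starts at Grade ≥2. SAP Section 10.1.4 counts worsening of a pre-treatment event as treatment-emergent. For such a subject, Grade ≤1 would demand recovery to better than the starting state. The reduction row already has this defect.

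**The case against.** The strongest reply is that the table is advisory and already cushioned, and much of that stands. Withholding is decided with the medical monitor. A lower-dose restart is written into the hold cell. A subject restarted at residual Grade 2, for whom full dose is inadvisable, meets the reduction row. Section 8.4 lets the investigator remove a subject at discretion, and lists a possibly or probably related SAE as a reason to discontinue. The rows also differ in action, complete interruption against continued dosing, so different thresholds could be deliberate. These routes let a careful investigator depart from the default, but they leave the default itself as written.

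Three stronger readings are tempting and are not supported:
- A reader might infer that sites have no rule if a held event returns. In fact, a return that makes dosing inadvisable meets the hold trigger again at Grade ≥3, or the reduction trigger at Grade ≥2. What is missing is a withdrawal sentence in the hold row.
- A reader might infer that a Grade 3 event, which meets both triggers, has no governing row. The wording largely settles this, since the hold should be done and the reduction only may be done.
- A reader might infer that subjects are being harmed. The Study Rationale in the synopsis describes the gastrointestinal events seen in volunteers as self-limited once dosing stops, so they are not evidence of harm at restart.

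**Conclusion.** The inconsistency is real and plain on the face of Table 4: the default for return to full dose is Grade ≤2 after the more severe event and Grade ≤1 after the less severe one, and only the reduction row states withdrawal on recurrence. It is a minor point that is cheap to put right.

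The documents give no expected rate of related Grade ≥3 events, so the number of subjects affected cannot be estimated. The practical contrast is also smaller than two tablets against one, because the reduction is optional and rests on the investigator's judgement. The conclusion assumes the natural reading of the reduction row, namely that full dose may resume only once the event has reached Grade ≤1.

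**What to change.** **(a) Recommended.** In the hold row, resume the original dose at Grade ≤1 or at the subject's pre-treatment grade. If the event is Grade 2 and above that level when dosing restarts, restart at one tablet on the reduction row's terms: up to 14 days, longer only with the medical monitor. If the pre-treatment grade was 3, agree the restart dose with the medical monitor. Add the same pre-treatment-grade wording to the reduction row. Otherwise the hold row would again be looser for NTDT subjects who enter with Grade ≥2 anemia. The one-tablet restart applies equally to placebo, so the blind is kept.

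**(b) Optional, and a trade-off.** Give the hold row a graded recurrence rule. For example, a related event that returns to Grade ≥3 after re-introduction of the original dose leads to withdrawal, while a lesser return goes to the reduction row or the medical monitor. The reduction row's sentence should not be copied as it stands: it names no grade, so a mild return could force withdrawal. Section 8.5.1 makes that costly ("Any subject who discontinues study drug dosing must also be withdrawn from the study").

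**(c) Optional.** State that the hold row governs first for Grade ≥3 events.

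**Cost.** Change (a) costs at most 14 of 504 tablets (2.8%) per affected subject, unless the medical monitor extends the one-tablet period. Withdrawals under (b) are not in that figure. Each one ends all remaining dosing and scheduled on-study observation, in a study whose primary objective is safety. As an illustration, withdrawal at Week 12 forgoes 24 × 7 × 2 = 336 tablets, or 336 / 504 = 66.7%. No new visits, procedures or tablet strengths are needed. Because the edits bear on subject safety, Protocol Section 15.1.1 requires IRB/IEC and regulatory approval before sites use them, so they should go in with the next amendment.
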